4.2.2.5 EDSS

[figure not shown]
The EDSS score and its change from baseline will be summarized by treatment and visit. Only the assessment not obtained during a relapse will be considered as a baseline value.

Patient count (%) based on EDSS change categories, i.e., improvement, stable, deterioration, will be presented. The analysis will consider only those patients who were evaluated up to the assessment time point in the analysis (e.g. only patients with ≥ 12 months of follow-up in the 12-month assessment of EDSS, etc.). Only scheduled assessments will be considered; intermediate missing values for a scheduled visit will be considered not free of the event.

The definition of the categories are as follows, depending on the baseline EDSS score:

- If baseline EDSS score ≤ 5.0 :
 - improvement: reduction from baseline ≥ 1.0 ;
 - stable: change from baseline between (inclusive) -0.5 to 0.5 ;
 - deterioration: increase from baseline ≥ 1.0
- If baseline EDSS score > 5.0 :
 - improvement: reduction from baseline ≥ 0.5 ;
 - stable: no change from baseline;
 - deterioration: increase from baseline ≥ 0.5

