Patients who prematurely discontinue study drug during the Core Phase should be encouraged to remain in the study. Patients who prematurely withdraw (PPW – Premature Patient Withdrawal) from the study for any reason should be scheduled for a final Visit 14 (EOS-CP) assessment at the time of discontinuation from study drug as outlined in [Table 6-1](#)). A follow-up visit should then be scheduled three months after the last dose of the study drug. If the patient is unable to return to the site for the Visit 14 / EOS-CP assessments, every effort should be made to contact the patient by telephone for safety evaluations during the 3 months

following the last dose of study drug, including a final contact at the 90-day point (3-month follow up).

Patients who prematurely discontinue study drug (SDD) during the Core Phase, and remain in the study will follow an abbreviated schedule of assessments (see [Table 6-2](#)). At the time of SDD, patients must complete the Visit 14 / EOS-CP assessments (as end of treatment assessments), followed by a 3-month follow-up visit prior to continuing in the abbreviated schedule of assessments. If a patient who is being followed in the abbreviated schedule of assessments prematurely withdraws from the study, the patient should be scheduled for a final visit (EOS-CP according to [Table 6-2](#)) at the time of study discontinuation.

Patients who have completed the Core Phase, as per [Table 6-1](#) or [Table 6-2](#), may be eligible to enter the long-term extension study ([Table 6-3](#)). Patients who complete the Core Phase on study drug, but choose not to enter the Extension Phase should return for a 3-month follow-up visit.

Patients who prematurely discontinue study drug (SDD) during the Extension Phase, may remain in the study and be followed at yearly visits (see [Table 6-2](#)). At the time of SDD, patients must complete the Visit 30 assessments (as end of treatment assessments), followed by a 3-month follow-up visit.

Table 6-2 Core Phase: Abbreviated schedule of assessments for patients with SDD

Phase	Double-blind Treatment Phase						
Visit No. ¹	8	9	10	11	12	13	14/ EOS-CP
Study month	6	9	12	15	18	21	24
Physical exam	X		X		X		X
Skin exam							X
[REDACTED]							
Pulmonary Function Tests	X		X		X		X
MS relapses	X	X	X	X	X	X	X
MS treatment/Concomitant medications/Steroids	X	X	X	X	X	X	X
EDSS	X	X	X	X	X	X	X
MRI	X		X		X		X
[REDACTED]							
Vital signs	X	X	X	X	X	X	X
Hematology/Blood chemistry	X		X		X		X
[REDACTED]							

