6.4.2 MS relapse

The initial assessment, management and reporting of MS relapse is made by the Primary Treating Physician.

MS relapse definition: appearance of a new neurological abnormality or worsening of previously stable or improving pre-existing neurological abnormality, separated by at least 30 days from onset of a preceding clinical demyelinating event (McDonald et al 2001). The abnormality must have been present for at least 24 hours and occurred in the absence of fever (< 37.5°C) or known infection.

Diagnosing MS relapses during the study: a patient may report symptoms indicative of a relapse at a scheduled visit or at any other time. Patients will be instructed to immediately contact the Primary Treating Physician if he/she develops new or re-occurring or worsening neurological symptoms. At each scheduled visit, the patient will also be asked whether any such symptoms have occurred. If a patient reports new neurological symptoms or worsening of previous symptoms, an unscheduled visit is to be planned as soon as possible, ideally within 7 days. During this visit, the treating physician will first assess whether the new/worsening neurological abnormality is consistent with the definition of MS relapse above. If so, the standard neurological examination (for the EDSS score) should be performed by the Independent Evaluating Physician (EDSS rater). If there is any doubt in the opinion of the treating physician, the default must always be to refer the case to the Independent Evaluating Physician to perform an EDSS rating.

During the Extension Phase the EDSS assessment needs to be completed by a qualified EDSS rater. Blinding of EDSS ratings is not required during the Extension Phase since all patients will be treated with fingolimod. However, it is highly recommended that the EDSS rater used in the Core Phase continues to monitor the EDSS in the Extension Phase for consistency of readings. If a rater change is required then adjudication/discussion between "Core Phase Rater" and "Extension Phase Rater" should be done if there are differences between the last Core Phase evaluation and the first Extension Phase evaluation. Co-ratings are also recommended. Every effort should be made for the rater to remain the same throughout the study.

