3.8.4.1 Nominal visits

Nominal visits (i.e., the visits as collected in the database) will be used for by-visit summaries of EDSS, MRI, [REDACTED] and ophthalmic exam (OCT). Data from unscheduled visits will not be summarized in by-visit summaries, unless otherwise specified.

For subjects who complete the study drug before the nominal 24 month visit, the EOT visit (Visit 777) will be remapped to the next scheduled visit.

For subjects who discontinue the study drug prematurely, the EOT visit (Visit 777) and the follow-up visit (Visit 501) are not timepoint specific visits and will be remapped based on the following rules:

- If these visits fall into a specific visit window and the corresponding scheduled visit is missing, then these visits will be remapped to be that scheduled visit. The visit windows are defined as within 5 days of the monthly scheduled visit (i.e., Visits 4, 5, 6 and 7), or within 10 days of the quarterly scheduled visit (i.e., Visits 8, 9, 10, 11, 12, 13 and 14).
- If these visits fall into a specific visit window and the corresponding scheduled visit (e.g., Visit X) is not missing, then these visits will be assigned a visit number with a decimal place where the visit number depends on whether the corresponding scheduled visit occurs before (e.g., Visit X.1 or Visit X.2 if Visit X.1 already exists etc.) or after these visits (e.g., Visit X-1.1 or Visit X-1.2 if Visit X-1.1 already exists etc.)
- If these visits do not fall into a specific visit window but fall in between 2 consecutive scheduled visit windows (e.g., between visit windows of Visit X and Visit X+1), then these visits will be assigned a visit number with a decimal place (e.g., Visit X.1 or Visit X.2 if Visit X.1 already exists etc.).

The remapped visits (e.g., Visit X) will be treated as nominal visits in the by-visit summaries.

For subjects who discontinue study drug prematurely and have the abbreviated visits, all the abbreviated visits (if different visit numbering is used) will be mapped to the corresponding regular visits and will be treated as nominal visits in the by-visit summaries.

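### SAP 4.2.2.5 applies a cumulative free-of-event missing-visit rule to a three-category EDSS table that has no defined event, so an earlier missed visit can override the observed score

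*SAP*

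**What the plan says.** SAP 4.2.2.5 plans two EDSS displays. The first summarises the score and its change from baseline by treatment and visit. The second is the category table: "Patient count (%) based on EDSS change categories, i.e., improvement, stable, deterioration, will be presented".

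For a baseline EDSS of 5.0 or less, improvement and deterioration each need a change of at least 1.0, and a change from -0.5 to 0.5 is stable. Above 5.0, a change of 0.5 in either direction is enough.

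Three further rules bear on the category table:

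- Denominator: "The analysis will consider only those patients who were evaluated up to the assessment time point in the analysis".
- Missing data: scheduled assessments alone are used, and "intermediate missing values for a scheduled visit will be considered not free of the event".
- Relapse: "Only the assessment not obtained during a relapse will be considered as a baseline value". No matching rule is given for post-baseline scores.

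The visit structure matters as well. Under Protocol Section 6, a patient who stops study drug and stays in the Core Phase completes the end-of-treatment assessments, "followed by a 3-month follow-up visit prior to continuing in the abbreviated schedule of assessments". Table 6-2 then schedules EDSS at every quarterly visit from Month 6 to Month 24. SAP 3.8.4.1, which covers EDSS, maps the end-of-treatment and follow-up visits to a missing quarterly visit only if they fall within 10 days of it. If they fall between two windows, "these visits will be assigned a visit number with a decimal place", and the quarterly visit stays empty.

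**The concern.** A category defined by the change from baseline at one visit needs only two scores: baseline and that visit. What happened at visits in between is irrelevant to it. The missing-data sentence belongs to a different kind of endpoint, in which a patient must be shown to be free of something at every visit up to the time point.

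Applied here, the sentence either replaces an observed score with an assumed event or leaves the programmer to decide what the event is. In the first case, part of what the table shows as worsening would reflect missed visits and stopping of study drug rather than disability. If discontinuation or attendance differed between arms, that difference would enter the table too.

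A smaller issue concerns relapses. Scores taken during a relapse are kept out of the baseline but not out of later visits, so a temporary rise can be set against a baseline that excludes such rises.

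**Working it through.** The plan gives no figure for this table, so there is none to reproduce. The check is textual, followed by three illustrative calculations whose assumptions are stated.

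**1. The rule against the categories.** Take a patient with baseline EDSS of 5.0 or less, a change of 0 at Month 12, and no Month 9 score. By the category definition the patient is stable at Month 12. By the missing-data sentence the patient is not free of an event. Both cannot hold if the event is deterioration. If the event is something else, the text does not say what.

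**2. Gap after stopping study drug.** The inputs are quarterly target days 90 days apart (SAP Table 3-4), a follow-up visit 90 days after the last dose (Protocol Section 6), and a mapping window of ±10 days (SAP 3.8.4.1). The assumptions are that the end-of-treatment visit falls on the stop day and that stop days are uniform over the interval. Let u be the days from the last quarterly visit to the stop. The next quarterly visit, at day 90, is filled only if

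- the end-of-treatment visit reaches its window: u ≥ 80; or
- the follow-up visit at u + 90 is still in its window: u + 90 ≤ 100, so u ≤ 10.

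It is unfilled for 10 < u < 80, which is 70/90 = 77.8%. Counted in whole days with inclusive windows, it is u = 11 to 79, or 69/90 = 76.7%. If the follow-up date itself varies uniformly by ±10 days, the share is about 80%. The patient then rejoins the quarterly schedule, so the gap is about one visit.

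**3. Sporadic missed visits.** With an assumed independent missing rate m per visit and k intermediate visits from Table 6-2, the share with at least one gap is 1 − (1 − m)^k, among patients followed to the time point.

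| Time point | Intermediate visits | m = 2% | m = 5% |
|---|---|---|---|
| Month 12 | Months 6, 9 (k = 2) | 4.0% | 9.8% |
| Month 24 | Months 6 to 21 (k = 6) | 11.4% | 26.5% |

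**4. Scores during a relapse.** The share of time in relapse is ARR × duration / 365.25. With the planning ARRs of 0.36 and 0.18 (Protocol 9.6) and an assumed duration of 30 to 90 days:

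- Interferon: 0.36 × 30/365.25 = 3.0% to 0.36 × 90/365.25 = 8.9%.
- Fingolimod: 0.18 × 30/365.25 = 1.5% to 0.18 × 90/365.25 = 4.4%.

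These are shares of time in relapse, not misclassification rates. For a baseline of 5.0 or less, an in-relapse score counts as deterioration only if it rises by at least 1.0. SAP Table 4-3 grades a 0.5-point rise as a mild relapse, and that stays in the stable category. A 1- or 2-point rise is moderate and meets the threshold.

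**The case against.** The best defence is that the sentence's referent may lie in material that is not visible. Figures are missing around the 4.2.2.5 heading, and rows of Table 4-4 just above are redacted. SAP 10.1.1.4 also lists a proportion free of new MRI activity that appears nowhere in the visible endpoint list, so the sentence may have been written for another endpoint. That is possible, but it does not rescue the table. The sentence stands inside the category-table paragraph, directly before the category definitions. A hidden definition of the event as deterioration would confirm the problem.

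Other limits stand:

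- A reader might infer that the SAP moves stable patients into deterioration. It does not say so; that follows only if the event is read that way.
- A reader might infer that every patient with a missed visit is affected. Patients not followed to the time point are outside the denominator, so early withdrawals are not counted as events. If the unfilled visit is itself the time point, it is not intermediate.
- A reader might infer that any relapse score counts as deterioration. It must meet the threshold and be taken at a scheduled visit. For new symptoms Protocol 6.4.2 says "an unscheduled visit is to be planned as soon as possible, ideally within 7 days", and the category table leaves unscheduled assessments out.
- A reader might infer that disability is shown nowhere else in the plan. The EDSS score and its change by visit are also summarised.
- Table 6-1 is not in the text, so the EDSS schedule before Month 6, and whether EDSS is taken at the Core Phase follow-up visit, are unknown.

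**Conclusion.** The point holds as a mismatch between a missing-data rule and the table it governs. Read with deterioration as the event, the rule overrides an observed stable or improved score because of an earlier gap. Read without a defined event, it cannot be programmed.

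The 77-78% describes stop days among patients who stop study drug and stay in the study. It rests on uniform stop dates, follow-up at exactly 90 days, and EDSS being recorded at both visits. The documents do not say how many such patients to expect, so no share of the whole trial follows from it. The figures for sporadic gaps depend on the assumed miss rates.

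A bias between arms is possible but not shown: the documents give no discontinuation or attendance by arm. The table is descriptive, and EDSS is neither the primary nor the key secondary endpoint. Alpha, power and the primary conclusion are untouched. The relapse point is secondary, and its effect on the category counts cannot be sized from the documents.

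**What to change.** In SAP 4.2.2.5, delete the missing-visit sentence for the category table, keeping the restriction to scheduled assessments. State that each patient is classified by the observed EDSS change at the visit of interest, whatever happened at earlier visits. Among patients followed to that time point, show those with no score there as a separate missing row. If the sentence was meant for another endpoint, move it there and name the event.

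For the secondary point, present the table with and without scheduled post-baseline scores taken during a relapse.

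The cost is one sentence removed, two or three added and one extra table version. No new data are needed, since relapses are already recorded in the eCRF. The version without in-relapse scores will classify slightly fewer patients at each visit.

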4.2.3 Efficacy subgroup analyses

Key efficacy variables data (including primary and key secondary variables, i.e., ARR (time-based) and ARR (subject-based), and annualized rate of the number of new/newly enlarged T2 lesions) will be summarized separately for the following subgroups based on demographic and baseline characteristics.

- 
- age \leq 12 yrs vs. >12 yrs subgroups
- Body weight at randomization visit \leq 40 kg vs. >40 kg
- Female vs. male subgroups
- Hispanic/Latino vs. non-Hispanic/Latino subgroups

5 Pharmacokinetic/pharmacodynamics evaluations

5.1 Population pharmacokinetic analysis

A population pharmacokinetic analysis will be used to characterize the key pharmacokinetic parameters in this patient population. Additionally, this analysis will also determine whether there are population covariates that affect the pharmacokinetics of fingolimod-P when administered to this patient population.

The effect of covariates on pharmacokinetic parameters will be explored. Covariates examined will include age, weight, gender, and ethnicity as well as comedications such as oral ketoconazole which has been shown to interact with fingolimod-P in adults (increase in fingolimod and fingolimod-P plasma concentrations). The choice of covariates to be included in the model will be guided by exploratory plots of random effects (inter-individual variability parameters) against covariates. Those that are judged to show evidence of a relationship with the random effects will be tested for entry into the model, using the likelihood-ratio test with $p < 0.05$. The final covariate model will be derived using a rigorous and acceptable model building procedure.

The above analysis will be performed by Pharmacometrics (PMX) group. The report analysis plan and results will be provided separately.

5.2 Population pharmacokinetic/pharmacodynamics analysis

Population PK/PD modeling approaches will be used to relate the individual fingolimod PK parameter estimates to key efficacy measurements (MRI-related, relapse-related). A modeling plan will be prepared before final clinical database lock providing details for the proposed PK/PD analysis. This modeling plan will be prepared and executed by PMX group. The report analysis plan and the results will be provided separately.

6 Safety evaluation

Safety assessments include adverse events, bradycardia (first dose) events, laboratory tests, vital signs, ECG, pulmonary function tests, ophthalmic examinations, Tanner stages (bone x-ray), skin assessments, and C-SSRS data.

All safety data will be summarized on the SAF set. Some safety data (AEs, vital signs, labs, PFTs and C-SSRS) will also be summarized on the follow-up set by time-window (days 1 to 45 after study drug discontinuation and more than 45 days after study drug discontinuation) to assess subjects' safety after discontinuation of the study drug.

Unless otherwise specified, safety assessments in core phase (core phase data defined in section 3.8.3) more than 45 days after the study drug discontinuation will not be included in the summaries on the safety set but will be considered in the summaries on the follow-up set.

Adverse events starting before the first dose date will be excluded from the adverse event.

Details of the safety data summaries will be provided in the sections below. All safety data will also be presented in the listings.

6.1 Adverse events

6.1.1 Adverse event start date imputation

To ensure that all reported AEs are summarized, a conservative approach will be taken to impute the AE start date when it is incomplete or missing.

1. If the year value is missing, it will be imputed as the treatment start date.

2. If the year value is less than the treatment start date year value, it will be imputed as the midmonth date (15MONYYYY) or as the midyear date (01JulYYYY) if the month is missing.
3. If the year value is greater than the treatment start date year value, it will be imputed as the month start date (01MONYYYY) or as the year start date (01JanYYYY) if the month is missing.
4. If the year value is equal to the treatment start date year value, it will be imputed as the midmonth date (15MONYYYY) if the month is less than the treatment start month or as the start month date (01MONYYYY) if the month is greater than the treatment start month. In case the month value is missing or equal to the treatment start month, it will be imputed as the date one day after treatment start date.

6.1.2 Adverse events

In this section, the term adverse event (AE) will refer to any entry on the adverse events eCRFs. All AEs will be coded using MedDRA.

AEs will be summarized on the SAF set by presenting, for each treatment group, the number and percentage of patients having any adverse event by primary system organ class (SOC) and preferred term (PT). AE summary will also be presented in the pre-pubertal (Tanner staging score <2) and young subjects (<=12 years) subgroups.

AEs that fulfill the risk search terms (defined in the case retrieval sheet) with RMP risk will be summarized by risk name and lower level terms. Severe AEs, serious AEs, drug related AEs, most common AEs, AEs leading to premature discontinuation of study drug, AEs requiring study drug interruption, and AEs requiring additional therapy will also be summarized and presented in a similar format as AEs. Summaries on the pre-pubertal subgroup will also be presented.

Since the patients will have various exposure duration to the study treatment, incidence rates (IRs) of AEs, i.e., incidence of AEs per 100 patient-years, will be summarized by primary organ class and preferred term. The incidence rates of AEs that fulfill the risk search terms with RMP risk will also be summarized. The IR is calculated as the number of patients experiencing at least one event in a particular category over the total patient-years “at risk” for that event multiplied by 100. For patients who have that adverse event, the time at risk is the time from first study dose to the first onset date of that adverse event. For patients who did not have that adverse event, the time at risk is the time from first study dose to

- the minimum between i) the last dose date of study medication in the core phase +45 days and ii) the final study phase visit date for those who do not enter the extension phase
- the final study phase visit date on study phase completion eCRF (i.e., the day before the first dose date in extension) for those who enter the extension phase.

Additionally, occurrence rates of AEs, i.e. occurrence of AEs per 100 patient year by primary organ class and preferred term will be summarized. The occurrence rates of AEs that fulfill the risk search terms with RMP risk will also be summarized. The occurrence rate of an event

is calculated as the number (n) of all such events that patients experience divided by the patient years (Ny), where patient years are calculated as the sum of the number of days on study drug of all patients divided by 365.25. The occurrence of AEs per 100 patient years, which is calculated as $n/Ny*100$, will be presented.

AEs will also be summarized on the follow-up set for the following time periods defined by days relative to study drug discontinuation: days 1 to 45 after study drug discontinuation and more than 45 days after study drug discontinuation.

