3.8.3 Definition of core phase data

After completing the core phase, subjects have the option to enter the extension study. All core phase data are entered in the database for core phase. All extension data will be entered in the database for extension phase.

For subjects who do not enter the extension study, all collected data will be considered as core phase data.

For subjects who enter the extension study, any measurement or event prior to the first dose of the extension study drug that is recorded on the core phase eCRF in the core phase database. For running records (e.g., adverse events), any event starting prior to the first extension study drug that is recorded on core phase eCRF in the core phase database.

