3.8.5 Safety data cutoff and visit windows for summaries on follow-up set

For safety summaries on the safety set, only core phase data (defined in 3.8.3) which are within 45 days (5 times the half-life of FTY720, 9 days) after the last dose of study drug. For safety summaries on the follow-up set, all core phase data, including assessments or events more than 45 days after the last dose of study drug in core phase, will be considered.

The time-windows below will be used in summaries on the follow-up set.

- 1) Day 1 to 45 after drug discontinuation
- 2) >Day 45 after drug discontinuation

For each of the time-window, assessments collected or events started during the specified day intervals after the last dose date will be used. The last dose date defined in Section 3.8.7 will be used to determine day windows.

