3.8.7 Last dose day of randomized study medication

The last dose date of the randomized study drug will be collected on three eCRFs:

- 1) The last date patient took study drug on the study phase completion eCRF,
- 2) The study drug discontinuation date on the study drug discontinuation eCRF, and
- 3) The last end date on the study drug administration record eCRF.

The last dose date recorded in the study phase completion eCRF (included in the CMP data panel with visit number 778) will be used.

4 Efficacy evaluation

Unless otherwise specified, all efficacy analyses will be based on the Full Analysis Set, following the intention-to-treat principle. Analysis of the primary efficacy variable will also be conducted on the per-protocol set, as well as the analyses on the key secondary variable. Treatment group estimates will be determined using least-squares means estimates.

All statistical models will be adjusted by the two randomization stratification factors: region and pubertal status reported in IVRS based on investigator's assessment. Pooling of regions with small patient count will be performed for better model fitting based on patient count in the region and geographic proximity. As a result, there will be three regions: East Europe, West Europe, rest of the regions (pooled by three small regions with <20 patients for each: Australia, Middle and South America, and North America). A stratification factor may also be considered to be removed from the model in presence of extremely small stratum with scarce information or given model converge problem.

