6.1.3 SAEs and DAEs

SAEs include death and non-fatal SAEs. All SAEs starting on or after the first dose date, including those starting more than 45 days after study drug discontinuation, will be included in the summaries on the safety set.

DAEs refer to AEs leading to permanent study drug discontinuation.

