6.1.6 Data summaries

Summaries on the SAF set by treatment group include:

[figure not shown]
- Incidence of AEs by SOC and PT
- Incidence of AEs that fulfill the risk search terms with RMP risk by risk name and level terms
- Incidence of AEs by SOC and PT and maximum severity
- Incidence of AEs related to study drug by SOC and PT
- Incidence rate of AEs per 100 patient years by SOC and PT
- Incidence rate per 100 patient years of AEs that fulfill the risk search terms with RMP risk by risk name and level terms
- Occurrence of AEs per 100 patient-years by SOC and PT
- Occurrence per 100 patient years of AEs that fulfill the risk search terms with RMP risk by risk name and level terms
- Incidence of AEs by PT
- Incidence of deaths by SOC and PT
- Incidence of non-fatal SAE by SOC and PT
- Incidence of SAEs that fulfill the risk search terms with RMP risk by risk name and level terms
- Incidence of AEs requiring study drug interruption by SOC and PT
- Incidence of AEs requiring additional therapy by SOC and PT
- Incidence of AEs leading to study drug discontinuation by SOC and PT
- Occurrence of SAEs by SOC and PT
- Occurrence of NSAEs by SOC and PT
- Incidence of AEs that fulfill the risk search terms with RMP risk by risk name, level terms (only for level 1 and level 2), and severity

[figure not shown]
Summaries on the follow-up set by treatment group include:

- Incidence of AEs by SOC and PT by time-window (days 1 to 45 after study drug discontinuation, and more than 45 days after study drug discontinuation)

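### SAP 6.1.2 puts no cap on time at risk for event-free extension entrants, so some AE incidence rates run slightly low if any entrant came off drug more than 45 days before the final core visit

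*SAP*

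**What the plan says.** **Denominator.** SAP 6.1.2 divides the number of patients with at least one event by total patient-years at risk. A patient with the event contributes time to first onset. A patient without it falls under one of two rules:

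- Not entering the extension: time ends at the earlier of last core dose + 45 days and the final study phase visit date.
- Entering the extension: time ends at "the final study phase visit date on study phase completion eCRF (i.e., the day before the first dose date in extension"). Last dose plays no part.

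**Numerator.** SAP 3.8.5 restricts safety-set summaries to "only core phase data (defined in 3.8.3) which are within 45 days" of the last dose. The opening of SAP section 6 repeats this: assessments "more than 45 days after the study drug discontinuation will not be included in the summaries on the safety set", with a proviso for anything specified differently elsewhere. SAP 6.1.3 makes an exception for SAEs, "including those starting more than 45 days after study drug discontinuation, will be included in the summaries on the safety set".

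**Tables concerned.** SAP 6.1.6 lists "Incidence rate of AEs per 100 patient years by SOC and PT" and a matching table for RMP-risk AEs among the safety-set summaries. It lists no incidence-rate table for non-serious AEs alone or for SAEs alone.

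**Who can be affected.** Patients who stop study drug are asked to stay in the core phase (SAP 4.2.1.2; Protocol section 6). Patients who complete the core off drug may enter the extension (Protocol section 4), and stopping for lack of efficacy is expressly allowed for (Protocol 4.2). No washout is needed after IFN β, glatiramer acetate or dimethyl fumarate (Protocol 5.5.7).

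**The concern.** The rates are reported because exposure differs between patients, so the events counted and the time counted should cover the same window. For non-entrants they do, as far as non-serious AEs go: both stop at last dose + 45 days. For an entrant who came off drug earlier than that, the denominator keeps running while the numerator is closed to non-serious AEs. Two patients with the same off-drug history then contribute different time at risk only because one of them later enrols in the extension. The SAP gives no reason for the difference. What is at stake is a modest understatement of some safety rates, which is the non-conservative direction.

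**Working it through.** **1. The plan's own figure.** SAP 3.8.5 derives the cutoff as 5 half-lives of 9 days: 5 × 9 = 45 days. This reproduces.

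**2. Entrants still on drug.** Protocol section 6 allows up to 14 days between Visit 14 and Visit 15 and asks that drug not be interrupted. Since 14 < 45, a cap would not bind, and these patients are unaffected.

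**3. Entrants off drug.** If last dose was g days before the final core visit and g > 45, the SAP adds g − 45 days in which no non-serious AE can be counted. A stopper reaches the abbreviated schedule only after a 3-month follow-up visit (Protocol section 6), which is already past day 45.

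**4. Size, rare AE.** Assumptions, because the documents give no counts: 95 per arm (the planned number), k off-drug entrants in the arm, all stopping at month 6 (0.5 y), and no late SAE. Core length D is varied because the core is flexible with no minimum (Protocol section 4; SAP 9.1).

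- Excess per patient = D − 0.5 − 45/365.25 = D − 0.623 years
- Understatement = k × excess / (95 × D)

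| Core length D | Excess (y) | k = 1 | k = 2 | k = 5 | k needed for 5% |
|---|---|---|---|---|---|
| 2.0 y | 1.377 | 0.72% | 1.45% | 3.62% | 6.9, so 7 |
| 1.5 y | 0.877 | 0.62% | 1.23% | 3.08% | 8.1, so 9 |
| 1.0 y | 0.377 | 0.40% | 0.79% | 1.98% | 12.6, so 13 |

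Stopping at month 12 with k = 5 gives 2.31% (D = 2.0) or 1.32% (D = 1.5).

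In absolute terms, take 10 patients with the event, k = 5 and D = 2.0. The SAP denominator is 95 × 2 = 190 PY, giving 5.26 per 100 PY. With the cap it is 190 − 5 × 1.377 = 183.1 PY, giving 5.46.

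**5. Size, common AE.** Take a constant hazard of 0.3 per year, k = 5, a stop at month 6 and cutoff c = 0.623 y. Let U = (1 − exp(−0.3D))/0.3 and C = (1 − exp(−0.3c))/0.3. SAP 6.1.2 does not say how to treat a patient whose first event is a late, uncounted one, so there are two cases:

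- Time stops at the late onset: 1 − (90U + 5C)/(95U) = 3.27%, 2.79% and 1.80% for D = 2.0, 1.5 and 1.0.
- The patient counts as event-free to D, which adds 5 × exp(−0.3c) × (D − c) to a base of 90U + 5C: 3.97%, 3.16% and 1.90%.

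**6. Cross-check on other assumptions.** Take 81 entrants per arm (half of the roughly 162 in Protocol 9.6), 14 non-entrants followed for half the core, a core of 1.5 to 2 years and true rates of 5 or 50 per 100 PY. If 2% of entrants are off drug with a 90-day gap, the understatement is 0.1% to 0.2%. If 5% are, with a 180-day gap, it is 0.6% to 1.1%. If 10% are, with a 365-day gap, it is 3.5% to 5.5%.

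**7. Direction when late SAEs exist.** SAP 6.1.3 keeps SAEs after day 45 on the safety set. For non-entrants, whose event-free time is capped, a late SAE adds to the numerator without matching time for the others, which pushes the rate up. In a category with late SAEs the two effects oppose each other, and the net sign cannot be fixed from the documents.

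**The case against.** **The entrant rule may be a deliberate exception.** The cutoff in SAP section 6 yields to anything specified elsewhere, and 6.1.2 gives entrants their own window. If their late AEs also counted, there would be no mismatch. This reading is possible but weak: 6.1.2 changes only the denominator, SAP 3.8.5 carries no such proviso, and where an exception is meant (SAEs, in 6.1.3) it is spelled out. It is a reason for moderate rather than high confidence.

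**The affected group may be very small.** This stands. Patients who stopped for safety reasons are barred from the extension (Protocol 4.2), other prohibited drugs need full washout (Protocol 5.5.8), and some drugs exclude at any time. The wording of the entrant rule also suggests that it was written with uninterrupted completers in mind.

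**Stronger readings a reader might infer:**

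- *Every AE incidence rate is biased low.* Not supported. The planned tables cover all AEs and RMP-risk AEs, and late SAEs can push the other way.
- *The comparison between arms is biased.* Not supported. Nothing in the documents says how off-drug entrants divide between arms.
- *SAE rates need their own tables and a window to the follow-up visit*, given that "For subjects who do not enter the extension study, all collected data will be considered as core phase data". Not supported. No SAE incidence-rate table is planned, and follow-up data after core database lock go to the extension report (Protocol 9.6; SAP 9.1).

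**Conclusion.** The point holds as a minor one, with moderate confidence. If any extension entrant stopped drug more than 45 days before the final core visit, the incidence rate is understated for every category with at least one counted event and no late SAE. Where late SAEs are counted, the direction is undetermined.

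The size rests on assumed patient numbers and stop times: about 0.4% to 3.6% for 1 to 5 such patients in an arm of 95 stopping at month 6, for a rare AE and a core of 12 to 24 months. With no such patients it is zero.

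Other safety outputs are untouched. Crude incidence, which Protocol 9.5.3 makes a main basis of the safety assessment, has no person-time. Occurrence rates use time on drug ("patient years are calculated as the sum of the number of days on study drug of all patients divided by 365.25"). Follow-up-set tables have their own windows. Nothing in the documents suggests that a safety conclusion would turn on this.

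**What to change.** In SAP 6.1.2:

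- Use one rule for every patient without a counted event, whether or not they enter the extension: time at risk ends at the earlier of last core dose + 45 days and the final study phase visit date.
- State that a patient whose first event is a non-serious AE starting more than 45 days after last dose is treated as event-free, with time ending at that same minimum and not at the late onset date.
- Footnote the incidence-rate tables to say that SAEs starting after day 45 are counted under SAP 6.1.3.

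Add no SAE incidence-rate tables and no follow-up-visit window.

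**Cost.** One changed rule, one clarification and one footnote. Both dates are already on the study phase completion eCRF: SAP 3.8.7 uses "The last dose date recorded in the study phase completion eCRF", and SAP 4.1.2 takes the final visit date from the same form. The stated rates rise slightly. The existing mismatch for late SAEs remains, and would then apply to entrants as well, which is why the footnote is needed.
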